6.0 ENTRY/RANDOMIZATION PROCEDURES

6.1 Entry Procedures

All randomizations will be done through the CCTG web-based, password-operated Electronic Data Capture (EDC) system. Complete details regarding obtaining a password, accessing the system and registering/randomizing patients will be provided at the time of study activation and will also be included in the “EDC Data Management Guidebook”, posted on the IND.232 trial specific web-site. If sites experience difficulties accessing the system and/or registering/randomizing patients please contact the help desk (link in EDC) or the IND.232 Study Coordinator.

All eligible patients enrolled on the study by the participating treatment centre will be assigned a serial number which must be used on all documentation and correspondence with CCTG.

The following information will be required:

- trial code (CCTG IND.232)
- patient's initials (may be coded)
- informed consent version date, date signed by patient, name of person conducting consent discussion and date signed
- confirmation of the requirements listed in Section 4.0, including dates of essential tests and actual laboratory values
- height and weight

6.2 Randomization

Randomization will be provided electronically. This is a parallel cohort phase II study. Patients will be randomized between two cohorts when both cohorts are enrolling. After the interim analysis, depending on the results, patients may be randomized to one of two cohorts, or a single cohort if one has closed.

At the time of randomization, all data reported within the Patient Enrollment folder must be accurate, complete and verifiable against source documentation. If a system query is issued indicating that the patient is not eligible, enrollment within the EDC system will not proceed. CCTG should be contacted for assistance if needed. Under no circumstances should inaccurate data be entered in order to permit randomization.

Note: The validity of results of the trial depends on the authenticity of and the follow-up of all patients entered into the trial. Under no circumstances, therefore, may an allocated patient's data be withdrawn prior to final analysis, unless the participant withdraws from the trial and requests that data collection/submission cease from the point in time of withdrawal.

All eligible patients admitted to the trial will be followed by the coordinating centre. It is the responsibility of the physician in charge to satisfy himself or herself that the patient is indeed eligible before requesting randomization.

All randomized patients are to be followed until death or until sites are informed by CCTG that further follow-up is no longer required. The follow-up requirements for ineligible patients are outlined in Section 5.1.

7.0 TREATMENT PLAN

Although the Canadian Cancer Trials Group acts as the coordinating agency for the trial, the responsibility for treatment of patients rests with the individual investigator.

In accordance with CCTG policy, protocol treatment is to begin within 5 working days of patient randomization.

7.1 Durvalumab and Tremelimumab Treatment Plan

7.1.1 Drug Administration

When durvalumab is given with tremelimumab, tremelimumab will be administered first. Durvalumab infusion will start approximately 1 hour after the end of tremelimumab infusion.

One cycle will be defined as 4 weeks. Tremelimumab will only be given for the first 4 cycles.

Arm	Agent(s)	Dose	Route	Duration	Schedule
1 & 2	Durvalumab	1500 mg	IV	60 min	Day 1 every 4 weeks
1	Tremelimumab	75 mg	IV	60 min	Day 1, cycles 1-4

Patients with a body weight of less than or equal to 30 kg should be dosed using a weight based dosing schedule. See Section 3.3.

7.1.2 Premedication

No routine premedication (e.g. for nausea) or prophylaxis for hypersensitivity is required. Management of symptoms should take place as necessary (see Appendix II). Premedication is not expected to be required. See Appendix II with respect to premedication of patients that have had a prior \leq Grade 2 infusion-related reaction. Details of any premedication or concomitant medication given to manage or prevent adverse events should be recorded on the electronic case report form (eCRF).

7.1.3 Patient Monitoring

Patients will be monitored before, during infusion and after the infusion of tremelimumab and durvalumab with assessment of vital signs as specified in section 5.0. A 1-hour observation period is recommended after the first infusion of durvalumab and tremelimumab. If no clinically significant infusion reactions are observed during or after the first cycle, subsequent infusion observation periods can be at the Investigator's discretion (suggested 30 minutes after each durvalumab and tremelimumab infusion).

Guidelines for management of infusion-related reaction are summarized in Appendix II.

All patients should be closely monitored according to guidelines in Section 5.0 and be advised to contact the treating centre in the case of significant toxicities.

7.1.4 Dose Adjustments

The major toxic effects of durvalumab or tremelimumab which are anticipated to limit dosing are hypersensitivity/ infusion related reactions and possible class related immune related AEs, based on the mechanism of action of durvalumab ± tremelimumab leading to T-cell activation and proliferation. Potential immune related AEs include pneumonitis, hepatitis, diarrhea/colitis and intestinal perforation, endocrinopathies (thyroiditis, hypo and hyperthyroidism, adrenal insufficiency, hypophysitis/hypopituitarism diabetes insipidus and Type 1 diabetes mellitus), nephritis, rash/dermatitis, pancreatitis, myocarditis, myositis/polymyositis and rare/less frequent irAEs including neuromuscular toxicities such as myasthenia gravis and Guillain-Barre syndrome. Other inflammatory responses that are rare with a potential immune-mediated etiology include, but are not limited to, pericarditis, sarcoidosis, uveitis and other events involving the eye (e.g. keratitis and optic neuritis), skin (e.g. scleroderma, vitiligo and pemphigoid), hematological (e.g. hemolytic anemia and immune thrombocytopenic purpura) and rheumatological (e.g. polymyalgia rheumatic and autoimmune arthritis) events, vasculitis, non infectious encephalitis or non infectious meningitis. It is possible that events with an inflammatory or immune mediated mechanism could occur in nearly all organs.

The guidelines that outline dose adjustments for these toxic effects can be found in Appendix II. If a patient experiences several adverse events and there are conflicting recommendations, please use the recommended dose adjustment that requires the greatest dose hold or discontinuation. Adverse events will be graded using the NCI Common Terminology Criteria for Adverse Events (CTCAE) (see Appendix V).

Dose adjustments (slowing/interruption of infusion rate, omission of a dose, or permanent discontinuation) will be made for hematologic and other adverse events.

If the infusion cannot be administered, it should be omitted until the next planned infusion.

The next cycle should not be given until the laboratory criteria in Section 4.1.9 are met and resolution of all drug related toxicity to \leq grade 2. Discuss with CCTG if asymptomatic/not felt to be clinically significant.

7.1.5 Management of Toxicity

See Appendix II for full details of toxicity management.

The following general guidance should be followed for management of toxicities:

1. Treat each of the toxicities with maximum supportive care (including slowing / interrupting / omitting the agent suspected of causing the toxicity where required).
2. If the symptoms promptly resolve with supportive care, consideration should be given to continuing the same dose of durvalumab ± tremelimumab along with appropriate continuing supportive care.
3. All dose modifications should be documented with clear reasoning and documentation of the approach taken.

In addition to the detailed toxicity management guidelines described in Appendix II, the following principles are suggested:

- Patient evaluation to identify any alternative etiology.
- In the absence of a clear alternative etiology, all events of an inflammatory nature should be considered to be immune-related.

- Symptomatic and topical therapy should be considered for low-grade events.
- For persistent (greater than 2 to 3 days) low-grade (Grade 2) or severe (Grade ≥ 3) events promptly start prednisone PO 1-2 mg/kg/day or IV equivalent.
- If symptoms recur or worsen during corticosteroid tapering (≥ 4 weeks of taper), increase the corticosteroid dose (prednisone dose [e.g. up to 2-4 mg/kg/day or IV equivalent]) until stabilization or improvement of symptoms, then resume corticosteroid tapering at a slower rate.
- More potent immunosuppressives (refer to individual sections of the immune related adverse event for specific type of immunosuppressive) should be considered for events not responding to systemic steroids.
- Discontinuation of study drug is not mandated for Grade 3 / Grade 4 inflammatory reactions attributed to local tumour response (e.g. inflammatory reaction at sites of metastatic disease, lymph nodes, etc.). Continuation of study drug in this situation should be based upon a benefit/risk analysis for that patient and be discussed with CCTG.

7.1.6 Management of Infusion Reactions

Guidelines for management of infusion-related reactions are summarized in Appendix II. The standard infusion times for both durvalumab and tremelimumab are 1 hour. However, if there are interruptions during infusion, the total allowed time should not exceed 8 hours at room temperature.

Study personnel must be trained to recognize and treat anaphylaxis. The study site must have immediate access to appropriate drugs and medical equipment to treat acute anaphylactic reactions, emergency resuscitation teams and equipment in addition to the ability to admit patients to an intensive care unit if necessary.

7.1.7 Dose Adjustments for Immune Related Adverse Events and Other (Non-Immune Related) Adverse Events Related to Study Therapy

Guidelines for dose modification and toxicity management of immune related and non-immune related adverse events are summarized in Appendix II.

Centres must contact CCTG in the event of severe event(s), especially when the use of drugs such as infliximab are considered.

7.2 Duration of Therapy

Treatment with durvalumab \pm tremelimumab (to a maximum of 4 doses, cycles 1-4) will continue until disease progression or unacceptable toxicity.

Exceptions to the duration of treatment for patients with continued response may be made after consultation with CCTG.

7.3 Concomitant Therapy

Details of any concomitant medications (prescription, non-prescription, or over-the-counter medications) taken by the patient at study entry and during protocol therapy must be recorded on the appropriate electronic case report forms (eCRFs).

7.3.1 Permitted

- Growth factors may be used according to centre policy to treat life threatening toxicity but cannot be used in place of protocol defined dose adjustments. Please consult CCTG in the case of patients experiencing multiple delays as exceptions may be made for patients who are benefitting from protocol therapy.
- Other supportive and palliative care (e.g. pain control) as required throughout the study.
- Anti-emetics or anti-diarrheal agents as required.
- Bisphosphonates / denosumab are permitted for the treatment of hypercalcemia, osteoporosis and prevention of skeletal related events for patients with bone metastases. However, the need to initiate or increase the dose of these therapies during the study will be considered as indicative of disease progression leading to the discontinuation of patient unless disease progression can be completely ruled out.

7.3.2 Not Permitted

- Cytokines;
- Other anti-cancer treatment;
- Other investigational therapy;
- Concurrent radiation treatment; (Note: if patients require palliative radiation or prophylactic radiation (e.g. of brain) consult CCTG for exception to this rule; protocol therapy will need to be held prior to and during the radiation).
- Corticosteroids IV or PO (except for the treatment of \geq grade 3 infusion reaction, treatment-related toxicity (See Appendix II), and nausea prophylaxis for chemotherapy). Note: Topical applications (e.g. rash), inhaled sprays (e.g. obstructive airways diseases), eye drops or local injections (e.g. intra-articular) are allowed. Patients who are on low oral doses of prednisone (5 mg BID or dexamethasone equivalent) must discontinue prior to study entry unless medically contraindicated.
- Live attenuated vaccines within 30 days of durvalumab dosing (i.e. 30 days prior to the first dose, during treatment with durvalumab and for 30 days post discontinuation of durvalumab. Inactivated vaccines, such as the injectable influenza vaccine, are permitted.

8.0 CRITERIA FOR MEASUREMENT OF STUDY ENDPOINTS

8.1 Definitions

8.1.1 Evaluable for adverse events. All patients will be evaluable for adverse event evaluation from the time of their first treatment.

8.1.2 Evaluable for response. All patients who have received at least one cycle of therapy and have their disease re-evaluated will be considered evaluable for response. Patients who exhibit objective disease progression prior to the end of cycle 1 are considered to be evaluable). Patients on therapy for at least this period and who meet the other listed criteria will have their response classified according to the definitions set out below *[Seymour 2017]*.

Response and progression will be evaluated in this study using the revised international criteria (1.1) proposed by the RECIST (Response Evaluation Criteria in Solid Tumours) committee *[Eisenhauer 2009]* as well as the modified iRECIST guidelines *[Seymour 2017]*. Investigators should note the different requirements for confirmatory scans as well as follow up for the two criteria.

See Section 10 for criteria for continuing treatment past RECIST 1.1 disease progression.

8.2 RECIST 1.1 Response and Evaluation Endpoints

Response and progression will be evaluated in this study using the revised international criteria (1.1) proposed by the RECIST (Response Evaluation Criteria in Solid Tumours) committee, as well as Immune-Related modified RECIST criteria. Investigators should continue treatment, as appropriate, in the absence of unacceptable toxicity, until unequivocal disease progression. This is particularly important for patients in whom pseudoprogression may have occurred. Follow up response assessments must be continued until unequivocal disease progression has occurred.

8.2.1 Measurable Disease. Measurable *tumour lesions* are defined as those that can be accurately measured in at least one dimension (longest diameter to be recorded) as ≥ 20 mm with chest x-ray and as ≥ 10 mm with CT scan or clinical examination. Bone lesions are considered measurable only if assessed by CT scan and have an identifiable soft tissue component that meets these requirements (soft tissue component ≥ 10 mm by CT scan). *Malignant lymph nodes* must be ≥ 15 mm in the short axis to be considered measurable; only the short axis will be measured and followed. All tumour measurements must be recorded in millimetres (or decimal fractions of centimetres). Previously irradiated lesions are not considered measurable unless progression has been documented in the lesion.

8.2.2 Non-measurable Disease. All other lesions (or sites of disease), including small lesions are considered non-measurable disease. Bone lesions without a measurable soft tissue component, leptomeningeal disease, ascites, pleural/pericardial effusions, lymphangitis cutis/pulmonis, inflammatory breast disease, lymphangitic involvement of lung or skin and abdominal masses followed by clinical examination are all non-measurable. Lesions in previously irradiated areas are non-measurable, unless progression has been demonstrated.

8.2.3 Target Lesions. When more than one measurable tumour lesion is present at baseline all lesions up to *a maximum of 5 lesions total* (and a maximum of *2 lesions per organ*) representative of all involved organs should be identified as target lesions and will be recorded and measured at baseline. Target lesions should be selected on the basis of their size (lesions with the longest diameter), be representative of all involved organs, but in addition should be those that lend themselves to *reproducible repeated measurements*. Note that pathological nodes must meet the criterion of a short axis of ≥ 15 mm by CT scan and only the *short axis* of these nodes will contribute to the baseline sum. All other pathological nodes (those with short axis ≥ 10 mm but < 15 mm) should be considered non-target lesions. Nodes that have a short axis < 10 mm are considered non-pathological and should not be recorded or followed (see 8.2.4). At baseline, the sum of the target lesions (longest diameter of tumour lesions plus short axis of lymph nodes: overall maximum of 5) is to be recorded.

After baseline, a value should be provided on the CRF for all identified target lesions for each assessment, even if very small. If extremely small and faint lesions cannot be accurately measured but are deemed to be present, a default value of 5 mm may be used. If lesions are too small to measure and indeed are believed to be absent, a default value of 0 mm may be used.

8.2.4 Non-target Lesions. All non-measurable lesions (or sites of disease) plus any measurable lesions over and above those listed as target lesions are considered *non-target lesions*. Measurements are not required but these lesions should be noted at baseline and should be followed as “present” or “absent”.

8.2.5 Response.

All patients will have their BEST RESPONSE from the start of study treatment until the end of treatment classified as outlined below:

Complete Response (CR): disappearance of *target* and *non-target* lesions and normalization of tumour markers. Pathological lymph nodes must have short axis measures < 10 mm (Note: continue to record the measurement even if < 10 mm and considered CR). Residual lesions (other than nodes < 10 mm) thought to be non-malignant should be further investigated (by cytology specialized imaging or other techniques as appropriate for individual cases [Eisenhauer 2009]) before CR can be accepted. Confirmation of response is required in this small randomized control trial.

Partial Response (PR): at least a 30% decrease in the sum of measures (longest diameter for tumour lesions and short axis measure for nodes) of target lesions, taking as reference the baseline sum of diameters. Non target lesions must be non-PD. Confirmation of response is required in this small randomized control trial.

Stable Disease (SD): Neither sufficient shrinkage to qualify for PR nor sufficient increase to qualify for PD taking as reference the smallest sum of diameters on study.

Progressive Disease (PD): at least a 20% increase in the sum of diameters of measured lesions taking as references the smallest sum of diameters recorded on study (including baseline) AND an absolute increase of $\geq 5\text{mm}$. Appearance of new lesions will also constitute progressive disease (including lesions in previously unassessed areas). In exceptional circumstances, unequivocal progression of non-target disease may be accepted as evidence of disease progression, where the overall tumour burden appears to have increased by at least 73% in volume or, in select instances where tumour burden has increased sufficiently to require urgent medical intervention (e.g. radiation for spinal cord compression or drainage of a fluid collection. Modest increases in the size of one or more non-target lesions are NOT considered unequivocal progression. If the evidence of PD is equivocal (target or non-target), treatment may continue until the next assessment, but if confirmed, the earlier date must be used.

Patients that are clinically well may continue on therapy following RECIST progression with new lesions or increase in target lesions if the increase in disease burden does not meet the definition of PD by immune response criteria [Seymour 2017]. In this situation, patients do not have unequivocal progression until immune response criteria are met (see Table 2 below).

Table 1: Integration of Target, non-Target and New Lesions into Response Assessment:

Target Lesions	Non-Target Lesions	New Lesions	Overall Response	Best Response for this Category also Requires
Target lesions \pm non target lesions				
CR	CR	No	CR	Normalization of tumour markers, tumour nodes $< 10\text{ mm}$
CR	Non-CR/Non-PD	No	PR	
CR	Not all evaluated	No	PR	
PR	Non-PD/ not all evaluated	No	PR	
SD	Non-PD/ not all evaluated	No	SD	Documented at least once ≥ 4 wks. from baseline
Not all evaluated	Non-PD	No	NE	
PD	Any	Any	PD	
Any	PD	Any	PD	
Any	Any	Yes	PD	
Non target lesions ONLY				
No Target	CR	No	CR	Normalization of tumour markers, tumour nodes $< 10\text{ mm}$
No Target	Non-CR/non-PD	No	Non-CR/non-PD	
No Target	Not all evaluated	No	NE	
No Target	Unequivocal PD	Any	PD	
No Target	Any	Yes	PD	
Note: Patients with a global deterioration of health status requiring discontinuation of treatment without objective evidence of disease progression at that time should be reported as "symptomatic deterioration". This is a reason for stopping therapy, but is NOT objective PD. Every effort should be made to document the objective progression even after discontinuation of treatment.				

8.3 iRECIST Response Assessment

Overall response will also be assessed using iRECIST [Seymour 2017]. Immunotherapeutics may result in infiltration of immune cells leading to transient increase in the size in malignant lesions, resulting in previously undetectable lesions becoming detectable. The criteria are identical to those of RECIST 1.1 in many respects but have been adapted to account for instances where an increase in tumour burden, or the appearance of new lesions, does not reflect true tumour progression.

Key differences are described below. All responses defined using iRECIST criteria are designated with a prefix. iRECIST time-point and best overall responses will be recorded separately.

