1.0 OBJECTIVES

1.1 Primary Objective

To determine the objective response rate (RECIST 1.1 and iRECIST) in patients with metastatic castration resistant prostate cancer (mCRPC) treated with durvalumab alone or in combination with tremelimumab.

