13.2 Primary Endpoints and Analysis

The primary endpoint of this study is the objective response rate, using iRECIST criteria defined in Section 8. Objective response rate using RECIST 1.1 will also be reported. 95% confidence interval for objective response rate in both definitions will be calculated.

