13.3 Sample Size and Duration of Study

A Simon's optimal two-stage design will be employed for both treatment arms. An objective response rate in either arm of 5% or less would not be of interest for further study (null hypothesis). If the objective response rate for either cohort were 20% or greater, then this would be considered of interest to further evaluate in larger trials (alternative hypothesis). Using an alpha error of 0.1 and a beta error of 0.1, 12 patients per arm will be initially accrued to stage 1. If 1 or more patients had objective response rate on either arm at end of stage 1, the arm will be expanded to a total of 37 evaluable patients. If ≥ 4 measurable responses are observed from these 37 patients in an arm then that arm would be considered for further testing in phase III trials.

If no objective response rates are observed in the first stage of an arm, then PD-L1 expression will be evaluated as a predictive biomarker, and expansion of that arm to 12 patients with PD-L1+ tumours will be considered. If fewer than 4 responses are seen after accrual to the second-stage of the study, then PD-L1 expression in biopsies will be evaluated and expansion of that arm to 37 patients with PD-L1+ tumours will be considered.

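### RECIST 1.1 best response is counted to the end of treatment with no stop at first RECIST 1.1 progression, so the RECIST 1.1 response rate can absorb responses meant to be specific to iRECIST

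*Combined protocol and SAP*

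**What the plan says.** The RECIST 1.1 response rate has a stated role. Section 1.1 gives the aim as "To determine the objective response rate (RECIST 1.1 and iRECIST". Section 13.2 makes the iRECIST rate primary ("The primary endpoint of this study is the objective response rate, using iRECIST criteria defined in Section 8") and adds "Objective response rate using RECIST 1.1 will also be reported", with a 95% confidence interval for each.

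The RECIST 1.1 counting window is in Section 8.2.5: "All patients will have their BEST RESPONSE from the start of study treatment until the end of treatment classified as outlined below". Table 3 in Section 8.3 gives iRECIST best overall response the same window.

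The last paragraph of Section 8.2.5 lets clinically well patients continue after RECIST progression if the immune criteria for PD are not met. It closes: "In this situation, patients do not have unequivocal progression until immune response criteria are met (see Table 2 below". Section 10.1 likewise keeps clinically stable patients with unconfirmed progression (iUPD) on treatment until the next assessment.

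Section 8.3.1 says that confirmation of progression is needed under iRECIST but not under RECIST 1.1. It also says that an earlier iUPD does not rule out a later iRECIST response.

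**The concern.** Reporting both rates is useful because the gap between them shows how many responses depend on the immune criteria. That requires the RECIST 1.1 count to stop where RECIST 1.1 says the disease has progressed. Section 8.2.5 sets no such stop, while treatment, scanning and response classification continue past that point. A response after progression can then enter both counts, and the gap shrinks for a reason that the reader of the results cannot see.

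The closing sentence of Section 8.2.5 adds a second ambiguity. It stands among the RECIST 1.1 definitions but points to an iRECIST table, and it does not say whether it concerns treatment or the recorded date of PD. Section 8.4 (response duration) and Section 13.1 (time to progression) do not say which progression event they use, so they do not settle it.

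**Working it through.** **1. The plan's own design figures.** Inputs from Section 13.3: null rate 0.05 ("An objective response rate in either arm of 5% or less would not be of interest for further study (null hypothesis"); alternative 0.20 ("If the objective response rate for either cohort were 20% or greater"); "Using an alpha error of 0.1 and a beta error of 0.1, 12 patients per arm will be initially accrued to stage 1"; an arm continues with at least 1 response, expands to 37, and is positive with at least 4.

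- P(stop at stage 1) = (1 − p)^12. At p = 0.05 this is 0.540.
- P(positive) = Σ over x = 1 to 12 of P(X₁ = x) × P(X₂ ≥ 4 − x), with X₁ ~ Bin(12, p) and X₂ ~ Bin(25, p). At p = 0.05 this is 0.0935; at p = 0.20 it is 0.902.
- Expected size under the null = 12 + (1 − 0.540) × 25 = 23.5.

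A search over two-stage designs up to n = 50 returns this one as optimal. The design reproduces, and the point does not concern it.

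**2. One patient traced through the rules.** Let S be the baseline sum of target lesions, with baseline as the smallest sum so far.

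- First scan: sum at least 1.20 × S and at least 5 mm above S, no new lesion. Section 8.2.5 and Table 1 give RECIST 1.1 PD. Table 2 gives iUPD.
- The patient is clinically stable. Sections 8.2.5 and 10.1 allow treatment to continue.
- Later scan: sum at most 0.70 × S, non-target disease not progressing, no new lesion present. Partial response is judged against baseline, so Table 1 returns PR. Table 2 returns iPR.
- A repeat scan confirms the response, as Section 8.2.5 requires.
- The patient is still on treatment, so this PR lies inside the Section 8.2.5 window. Nothing in Section 8.2 says that the earlier PD bars it.

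RECIST 1.1 best response is therefore PR. With a stop at first PD it would be PD. The iRECIST best response is iPR either way.

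**3. Size.** Each such patient shifts an arm's RECIST 1.1 rate by 1/37 = 2.7 points. The documents give no frequency for responses after RECIST 1.1 PD, so the number per arm is an assumption:

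| Such patients in 37 | Shift in RECIST 1.1 rate |
|---|---|
| 0 | 0 |
| 1 | 2.7 points |
| 2 | 5.4 points |
| 3 | 8.1 points |

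With one such patient, a reported 4/37 = 10.8% (exact 95% CI 3.0 to 25.4) would be 3/37 = 8.1% (1.7 to 21.9) under a window ending at first PD.

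**4. After the change.** Stage 1 stays at 12, the total at 37, alpha at 0.0935 and power at 0.902, because the primary endpoint is the iRECIST rate.

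**The case against.** The strongest reply is that the plan keeps the two sets of criteria apart. RECIST 1.1 PD is defined in Section 8.2.5 with no immune condition, and Table 1 returns PD at any scan with a new lesion. Section 8.3.1 states the difference on confirmation, Section 8.3 records iRECIST responses separately, and a footnote to Table 2 says that the response categories agree if there is no pseudoprogression, which implies that they may otherwise differ. All of this stands. A reader might infer that RECIST 1.1 collapses into iRECIST, and these passages do not support that. They do not close the gap either: separate recording does not say which scans count toward RECIST 1.1 best response.

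A reader might also infer that the sentence on unequivocal progression moves the RECIST 1.1 PD date by 4 to 8 weeks (the confirmation window) or by 12 weeks (the scan interval). The documents do not establish this. The sentence before it already calls the event RECIST progression. Section 8.2 uses the term unequivocal progression for how long to continue treatment and assessments. Section 8.2.5 also dates equivocal PD that is later confirmed back to the earlier scan.

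A third tempting inference is a higher chance of a false positive result. If 3 to 5 points were added to a true 5% rate, the chance of passing the 4-of-37 rule would rise from 0.0935 to 0.294 (at 8%) or 0.447 (at 10%). The arithmetic is right, but it applies the rule to a supportive count. Section 13.3 names no criterion, and with iRECIST primary in Section 13.2 the natural reading is that the rule uses iRECIST. The 3 to 5 points also have no source in the documents.

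Finally, Sections 8.1.2 and 8.2 adopt the published RECIST 1.1 criteria by reference, which might supply a cut-off. That cannot be checked from the documents. For the same reason, no claim is made here about comparability with other trials' RECIST 1.1 results. The window that the protocol itself states has no cut-off.

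**Conclusion.** The point holds as a gap in the definition of a reported endpoint. Under the Section 8.2.5 window, the RECIST 1.1 rate can include responses that follow RECIST 1.1 PD. The size is 2.7 points per such patient in an arm of 37, and the number of such patients is unknown. It rests on reading the Section 8.2.5 window as written and on such patients staying on treatment until the response is confirmed.

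The affected result is the RECIST 1.1 response rate, which is named in the primary objective and reported with its own confidence interval. Response duration and time to progression are ambiguous as to which progression event counts, but no shift in either is shown. The primary iRECIST rate and the two-stage design are not affected, and no numerical error was found.

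**What to change.** Three clarifications:

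1. In Section 8.2.5, state that RECIST 1.1 best response is taken up to and including the first RECIST 1.1 PD, whether or not treatment continues.
2. In the last paragraph of Section 8.2.5, state that the sentence on unequivocal progression concerns only the continuation of treatment and assessments and does not change the RECIST 1.1 PD date.
3. In Section 8.4 for response duration, and in Section 13.1 for time to progression, name the progression event used (RECIST 1.1 PD or the iRECIST event).

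The cost is a few sentences. The scans and time-point assessments are already collected, and neither the sample size nor any treatment rule changes. The downside is that the reported RECIST 1.1 response rate may be slightly lower.
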